6.4.4 Overdose Instructions

Study drug overdose is the accidental or intentional use of the drug in an amount higher than the dose being studied. An overdose or incorrect administration of study drug is not an AE unless it results in untoward medical effects.

Any study drug overdose or incorrect administration of study drug should be noted on the Study Drug Administration electronic case report form (eCRF).

All AEs associated with an overdose or incorrect administration of study drug should be recorded on the Adverse Event eCRF. If the associated AE fulfills serious criteria, the event should be reported to the sponsor immediately (i.e., no more than 24 hours after learning of the event).

For any subject experiencing an acalabrutinib overdose, observation for any symptomatic side effects should be instituted, and vital signs and biochemical and hematologic parameters should be followed closely (consistent with the protocol or more frequently, as needed). Appropriate supportive management to mitigate adverse effects should be initiated. If the overdose ingestion is recent and substantial, and if there are no medical contraindications, use of gastric lavage or induction of emesis may be considered.

Subjects who experience an overdose of venetoclax should be closely monitored and provided appropriate supportive treatment. During the ramp-up phase, interrupt venetoclax and monitor carefully for signs and symptoms of TLS along with other toxicities. Based on venetoclax large volume of distribution and extensive protein binding, dialysis is unlikely to result in significant removal of venetoclax.

6.4.5 Hepatitis B Virus Reactivation

Cases of HBV reactivation have been reported in patients treated with acalabrutinib with one case resulting in liver failure and death. Any subject with a rising viral load (above lower limit of detection: approximately 10 IU/mL) should discontinue study treatment, have antiviral therapy instituted, and have a consultation with a physician with expertise in managing hepatitis B. Patients who are anti-HBc positive may receive prophylactic antiviral agents while undergoing CLL therapy, per institutional guidelines.

Refer to the Schedule of Activities for frequency and duration of HBV monitoring.

6.4.6 Progressive Multifocal Leukoencephalopathy

Cases of PML have been reported in patients treated with acalabrutinib. Signs and symptoms of PML may include cognitive and behavioral changes, language disturbances, visual disturbances, sensory deficits, weakness, and coordination and gait difficulties.

If PML is suspected, hold further treatment with acalabrutinib treatment until PML is excluded. A diagnostic evaluation may include (but is not limited to):

- Neurologic consultation
- Brain magnetic resonance imaging (MRI)
- PCR analysis for John Cunningham virus DNA in cerebrospinal fluid

If PML is confirmed, permanently discontinue acalabrutinib.

[figure not shown]
6.4.7 Elevated Liver Function Tests

Subjects should be monitored for increases in liver biochemistry indicating potential Hy's law (PHL) or Hy's law (HL). The investigator is responsible for determining whether a subject meets PHL criteria at any point during the study. The process to be followed in identifying and reporting cases of PHL and HL is summarized in [Appendix 3](#).

6.5 Phase 1b Dose Escalation Portion

[Figure 1](#) depicts the dose escalation schema Cohorts 1 and 2 of this study.

Figure 1: Phase 1b Dose Escalation Schema for Cohorts 1 and 2

As this combination has not previously been evaluated in a clinical trial, a toxicity assessment will occur after the first 6 subjects with relapsed/refractory CLL have been accrued to dose level 1. At this time, accrual will be held until all subjects are followed for 8 weeks (2 cycles). Toxicities will then be reviewed by the principal investigator. If, during this time, there is ≤ 1 DLT (outlined below), Phase 1b expansion will begin for Cohort 1. If more toxicity than expected is observed and there are 2 or more DLTs in this group, the next 3 to 6 subjects will be

accrued at [REDACTED] and this group will be monitored until all have completed [REDACTED] of therapy. If there are 2 or more DLTs in this group, 3 to 6 subjects will be accrued at [REDACTED]

[REDACTED] The highest dose level at which less than 2/6 subjects experience DLT will be the recommended Phase 1b expansion dose. Once the Phase 1b dose-escalation portion is complete for Cohort 1 and dose level is established, this cohort will open to full accrual and Cohort 2 will open enrollment for 6 subjects at the recommended Phase 1b expansion dose for Cohort 1. A safety analysis for Cohort 2 will be performed after the first 6 subjects are followed for at least 8 weeks (2 cycles). The Acerta Review Committee will discuss the data in conjunction with the principal investigator and, once safety is established in this cohort, Cohort 2 will open for full Phase 1b expansion.

Dose-limiting toxicity will be defined as the following toxicities related to protocol therapy during the first [REDACTED] of therapy:

- \geq Grade 3 nonhematologic toxicity lasting for \geq 7 days
- \geq Grade 3 prolongation of the QTc interval
- Grade 4 neutropenia (ANC <500/ μ L) lasting \geq 7 days after discontinuation of therapy without growth factors or lasting \geq 5 days after discontinuation of therapy while on growth factors in subjects with pre-treatment ANC \geq 1 \times 10⁹/L
- \geq Grade 3 febrile neutropenia
- Grade 4 thrombocytopenia (platelet count <20,000/ μ L) lasting \geq 7 days after discontinuation of therapy or requiring transfusion in subjects with pretreatment platelet count >50,000/ μ L.
- Dose delay due to toxicity for >14 consecutive days

Prior to amending dosing from [REDACTED] the 6 subjects in the relapsed/refractory disease cohort had been enrolled. Since the new dose is the same daily dose of acalabrutinib, the previously accrued safety cohort can still be used to evaluate toxicity of the combination.

Table 4: Dose Levels for Phase 1b Dose Escalation Portion for Cohorts 1 and 2

Dose level	Acalabrutinib	Obinutuzumab
cc1		

6.6 Phase 1b Expansion Portion for Cohorts 1 and 2

For both Cohort 1 and Cohort 2, after 6 subjects have been treated in the Phase 1b dose-escalation portion and followed for 8 weeks (2 cycles) with ≤ 1 DLT in Cohort 1 and satisfactory safety observed in Cohort 2, this dose level will be considered the recommended Phase 1b expansion dose and that cohort of the study will open to full accrual.

6.7 Duration of Therapy

For Cohorts 1 and 2, acalabrutinib treatment can continue until the end of study for subjects without disease progression and who are tolerating therapy. The end of study is defined as 36 cycles after the last subject is enrolled to allow for long term follow-up beyond 36 cycles.

For Cohorts 3 and 4, protocol therapy with obinutuzumab or rituximab will continue for up to cc1 (until the end of cc1 in responding subjects. Subjects will discontinue venetoclax at the end of cc1. Treatment with acalabrutinib is continued until evidence of disease progression, toxicity, or end of study, whichever occurs first. Acalabrutinib; however, can be discontinued by investigator decision after cc1 in subjects with CR/CRi and/or negative MRD.

cc1

In Cohorts 1 and 2, subjects who achieve a bone marrow MRD-negative CR have the option to discontinue acalabrutinib.

Subjects who are still on treatment at the end of study and deriving clinical benefit from acalabrutinib monotherapy may continue treatment. At the time of the final data cutoff (DCO)

and database closure, subjects who remain in the study may be transitioned to a separate rollover study or remain within this study for continued access to study drug. Once all active subjects are eligible to continue to receive acalabrutinib and after database closure, this study will be considered closed. There will be no further data collection other than reporting of SAEs per [Section 10.5](#). Access within this study will enable continued treatment with visit assessments per standard of care, whereas the separate rollover study will enable treatment continuation with visit assessments and data collection per the rollover study protocol.

See [Section 7](#) for dose modifications and [Section 11](#) for criteria for removal from the study.

7 Dose Adjustments and Modifications

7.1 Subject Monitoring and Dose Modifications

7.1.1 Obinutuzumab

Please refer to the GAZYVARO prescribing information for subject monitoring during infusion and management of infusion reactions.

7.1.1.1 Obinutuzumab Dose Modification and Discontinuation

Refer to [Section 7.2](#) for dose adjustments for toxicities relating to obinutuzumab.

7.1.2 Venetoclax

Venetoclax Dose Modifications Based on Toxicities

Please refer to the VENCLEXTA® prescribing information for recommendations regarding dose modifications for toxicity and [Section 7.1.2](#) and [Section 7.2](#).

7.1.3 Rituximab

7.1.3.1 Subject Monitoring During Infusion

Refer to RITUXAN® prescribing information.

7.1.3.2 Management of Infusion Reactions with Rituximab

Management of infusion reactions are per RITUXAN® prescribing information and [Section 7.2.2.1](#).

7.1.3.3 Rituximab Dose Modification and Discontinuation

Dose modification of rituximab is not recommended; please refer to the RITUXAN® prescribing information and [Section 7.1.2](#) and [Section 7.2](#) for details. If rituximab is discontinued, subjects can continue acalabrutinib and venetoclax as outlined in the protocol. If acalabrutinib or venetoclax is discontinued, a subject may continue to receive rituximab up to the maximum number of infusions as outlined in the protocol.

The US Prescribing Information for rituximab will serve as Reference Safety Information (RSI) for this study to facilitate determination of expectedness or unexpectedness of AEs possibly associated with rituximab.

7.2 Dose Adjustment and Management of Toxicity for Phase 1b After **CCI** and Phase 1b Expansion Phase, and Phase 1b Venetoclax Cohorts

This section describes management of hematologic and nonhematologic toxicities for subjects in the Phase 1b dose-escalation portion after **CCI** subjects in Cohorts 1 and 2 in the Phase 1b expansion portion. This section also describes management of hematologic and nonhematologic toxicities in the Phase 1b portion wherein venetoclax is added during **CCI** (Cohorts 3 and 4).

7.2.1 Dose Adjustments for Hematologic Toxicity

7.2.1.1 Cohorts 1 and 2

Hematologic toxicity will be graded according to the IWCLL 2008 guidelines ([Hallek et al. 2008](#)).

Table 5: IWCLL 2008 Grading for Hematologic Toxicity

Grade	Decrease in Platelets ^a or HGB ^b from Pretreatment Value	Absolute Neutrophil Count (μ L) ^c
1	11% to 24%	≥ 1500 and <2000
2	25% to 49%	≥ 1000 and <1500
3	50% to 75%	≥ 500 and <1000
4	$\geq 75\%$	<500

^a Platelet counts must be below normal levels for any grade toxicity to be recorded. If platelet count is $<20 \times 10^{12}/L$, this will be considered Grade 4 toxicity.

^b Hgb levels must be below normal levels for any grade toxicity to be recorded.

^c If ANC is <1000 prior to study, the patient is not evaluable for toxicity assessment based on ANC.

During Cycle 1, laboratory parameters will be monitored according to the Schedule of Assessments and will be used in the evaluation of hematologic toxicities. Beginning Cycle 8, laboratory parameters will be monitored monthly and used in the evaluation of hematologic toxicities. If subjects experience Grade ≥ 3 hematologic toxicity, febrile neutropenia, or significant bleeding attributable to study drug, acalabrutinib should be held until toxicity resolves to \leq Grade 1 or to baseline. For the first occurrence, acalabrutinib may be restarted at the same dose level **CCI** however, for the second occurrence acalabrutinib should be restarted at **CCI**

Granulocyte colony-stimulating factor (G-CSF) and granulocyte-macrophage colony-stimulating factor (GM-CSF) may not be used prophylactically but may be used at the treating physician's

discretion in subjects with neutropenia related to obinutuzumab or acalabrutinib who are otherwise tolerating therapy and responding well.

Table 6: Dose Adjustments During [REDACTED] CCI [REDACTED] CCI [REDACTED]

Phase 1b Expansion Subjects Only During [REDACTED] CCI [REDACTED]

All Subjects During [REDACTED] CCI [REDACTED]

Dose Level	Acalabrutinib Dose	Obinutuzumab Dose
CCI		

For any Grade ≥ 3 hematologic toxicity, febrile neutropenia, or clinically significant bleeding attributable to study drug, obinutuzumab and acalabrutinib should be held and complete blood count (CBC) monitored weekly. When toxicity resolves to \leq Grade 1 or to baseline, study drugs should be resumed with 1 dose level reduction (obinutuzumab to restart at the next cycle). If subjects are stable at a reduced dose level for [REDACTED] CCI [REDACTED] dose escalation can occur by 1 dose level.

7.2.1.2 Cohorts 3 and 4

During Cycle 1, laboratory parameters will be monitored weekly and will be used in the evaluation of hematologic toxicities. Beginning Cycle 4, laboratory parameters will be monitored on Day 1 of each cycle, while on Cycle 7 results will be monitored Day 1 every 3 cycles. Results will be used in the evaluation of hematologic toxicities.

If subjects experience Grade ≥ 3 hematologic toxicity, febrile neutropenia, or significant bleeding attributable to study treatment within Cycles 1 and 2, acalabrutinib should be held until toxicity resolves to \leq Grade 1 or to baseline. For the first occurrence, acalabrutinib may be restarted at the same dose level [REDACTED] CCI [REDACTED] however, for the second occurrence acalabrutinib should be restarted at [REDACTED] CCI [REDACTED]

After start of venetoclax in [REDACTED] CCI [REDACTED] for any Grade ≥ 3 hematologic toxicity, febrile neutropenia, or clinically significant bleeding attributable to study treatment, recommendations regarding dose interruptions or modifications should be applied to venetoclax first. Recommendations are provided in the current prescribing information for venetoclax (please refer to [Table 9](#) for venetoclax dose reduction guidelines). Consider discontinuing venetoclax for subjects who require dose reductions to less than [REDACTED] CCI [REDACTED] for more than [REDACTED] CCI [REDACTED]

If subjects continue to experience Grade ≥ 3 hematologic toxicity, febrile neutropenia, or significant bleeding, please follow the recommendations for acalabrutinib as noted for **CCI**

G-CSF and GM-CSF may not be used prophylactically but may be used at the treating physician's discretion in subjects with neutropenia related to obinutuzumab, rituximab, venetoclax, or acalabrutinib who are otherwise tolerating therapy and responding well.

Missed doses of either drug should not be made up.

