3.1 Inclusion Criteria

1. Subjects with a diagnosis of intermediate or high risk CLL (or variant immunophenotype), SLL, or B-cell prolymphocytic leukemia (B-PLL) by IWCLL 2008 criteria ([Hallek et al. 2008](#)) who have:
 - Cohorts 1 and 3: Previously received at least 1 therapy for their disease (Cohort 3 enrollment limited to CLL).
 - Cohort 2: Previously untreated disease and ≥ 65 years old OR under 65 years old and refuse or are ineligible for chemoimmunotherapy.
 - Cohort 4: Previously untreated disease; Cohort 4 enrollment limited to CLL.

2. Subjects in Cohorts 1 and 3 may have received previous ibrutinib (or another BTK inhibitor) as long as discontinuation was for a reason other than on-treatment disease progression.
3. All subjects must satisfy one of the following criteria for active disease requiring therapy:
 - Evidence of marrow failure as manifested by the development or worsening of anemia or thrombocytopenia (not attributable to AIHA or thrombocytopenia)
 - Massive (≥ 6 cm below the costal margin), progressive or symptomatic splenomegaly
 - Massive nodes (≥ 10 cm) or progressive or symptomatic lymphadenopathy
 - Constitutional symptoms, which include any of the following:
 - Unintentional weight loss of 10% or more within 6 months
 - Significant fatigue limiting activity
 - Fevers $\geq 100.5^{\circ}\text{F}$ for 2 weeks or more without evidence of infection
 - Night sweats >1 month without evidence of infection
4. This criterion was removed with Amendment 5.
5. Subjects with a history of Richter's syndrome are eligible if they now have evidence of CLL only, with $<10\%$ large cells in the bone marrow.
6. Subjects must have adequate organ function, defined as creatinine ≤ 2.5 times the upper limit of normal (ULN), alanine aminotransferase (ALT) and aspartate aminotransferase (AST) $\leq 3.0 \times$ ULN, and bilirubin $\leq 2.5 \times$ ULN. For Cohorts 3 and 4, subjects must have creatinine clearance ≥ 50 mL/min using modified Cockcroft-Gault equation (using Ideal Body Mass [IBM] instead of mass):
7. IBM (kg) = $[(\text{height cm} - 154) \bullet 0.9] + (50 \text{ if male, } 45.5 \text{ if female})$.
8. Platelets $\geq 50 \times 10^9/\text{L}$. In subjects with CLL involvement of the marrow, $\geq 30 \times 10^9/\text{L}$ for Cohorts 1 and 2. For Cohorts 3 and 4, subjects must have hemoglobin $>9 \text{ g/dL}$.

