9.0 Important Protocol deviations

Important protocol deviation (IPD) categories are defined and managed by the study team during the IPD reviews throughout the study before database lock. These definitions of IPD categories, subcategory codes, and descriptions will be used during the course of the study. The final IPD list is used to produce the summary table and by-subject listing for IPDs.

10.0 demographics and baseline disease characteristics

The following variables collected at baseline will be presented:

- Demographics and baseline characteristics
 - Age (years)
 - Descriptive statistics
 - <65 vs. ≥65 years
 - <70 vs. ≥70 years
 - Sex (male, female)
 - Race
 - American Indian/Alaskan Native, African American/Black, Asian, Caucasian/White, Native Hawaiian/Other Pacific Islander or Other
 - Ethnicity (Hispanic or Latino, Non-Hispanic or Latino)
 - Height
 - Weight
 - Region (single site, United States)
 - ECOG performance status
- Baseline disease characteristics
 - Histology
 - For RR, TN
 - CLL
 - SLL

■ PLL

- Time since initial CLL diagnosis to first dose (years)
- Rai stage – Rai stage collected on the electronic case report form (eCRF) and derived Rai stage based on variables collected at screening visit using the criteria described in [Appendix B](#)
- Bulky disease (not applicable for RS/PLL) – defined as if at least one dimension of the lymph node measurement is
 - ≥ 5 cm
 - ≥ 10 cm
- B symptoms – weight loss, fever, night sweats, significant fatigue
- Chromosomal abnormalities
 - del(17)(p13.1) (TP53)
 - del(11)(q22.3) (ATM)
- β 2-microglobulin
 - >3.5 vs. ≤ 3.5 mg/L
 - >3 vs. ≤ 3 mg/L
- Number of prior systemic therapy
 - Descriptive statistics
 - <3 vs. ≥ 3
- Type of prior systemic therapy
- Time since most recent therapy (months)
- Cytopenia
 - Absolute neutrophil count (ANC) $\leq 1.5 \times 10^9/L$
 - Hemoglobin $\leq 11\text{g/dL}$
 - Platelet $\leq 100 \times 10^9/L$
 - Hemoglobin $\leq 11\text{g/dL}$ or platelet $\leq 100 \times 10^9/L$
 - Any of the above
- ANC ($10^9/L$)
- Absolute lymphocyte count (ALC) ($10^9/L$)
- Hemoglobin (g/dL)

- Platelets ($10^9/L$)
- IGHV mutation status (Unmutated IgHV, Mutated IgHV)
- ZAP-70 Methylation Status (Positive, Negative, Not Done/NA)
- Complex Karyotype
 - Subjects with complex karyotype
 - Subjects without complex karyotype

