Appendix C: Grading Scale for Hematologic Toxicity in CLL (Hallek 2008)

Grade ¹	Decrease in platelets ² or Hb ³ (nadir) from pretreatment value	Absolute neutrophil count/ μ L ⁴ (nadir)
0	No change to 10%	≥ 2000
1	11%-24%	≥ 1500 and < 2000
2	25%-49%	≥ 1000 and < 1500
3	50%-74%	≥ 500 and < 1000
4	$\geq 75\%$	< 500

1. Grades: 1, mild; 2, moderate; 3, severe; 4, life-threatening; 5, fatal. Death occurring as a result of toxicity at any level of decrease from pretreatment will be reported as Grade 5.
2. Platelet counts must be below normal levels for Grades 1 to 4. If, at any level of decrease, the platelet count is $< 20 \times 10^9/L$ (20,000/ μ L), this will be considered Grade 4 toxicity, unless a severe or life-threatening decrease in the initial platelet count (e.g., $< 20 \times 10^9/L$ [20,000/ μ L]) was present pretreatment, in which case the patient is not evaluable for toxicity referable to platelet counts.
3. Hemoglobin (Hb) levels must be below normal levels for Grades 1 to 4. Baseline and subsequent Hb determinations must be performed before any given transfusions. The use of erythropoietin is irrelevant for the grading of toxicity but should be documented.
4. If the ANC reaches $< 1 \times 10^9/L$ (1000/ μ L), it should be judged to be Grade 3 toxicity. Other decreases in the white blood cell count or in circulating neutrophils are not to be considered because a decrease in the white blood cell count is a desired therapeutic endpoint. A gradual decrease in granulocytes is not a reliable index in CLL for stepwise grading of toxicity. If the ANC was $< 1 \times 10^9/L$ (1000/ μ L) before therapy, the patient is not evaluable for toxicity referable to the ANC. The use of growth factors such as granulocyte colony-stimulating factor (G-CSF) is not relevant to the grading of toxicity but should be documented.

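### Protocol Table 5 footnote a (Cohorts 1 and 2) prints the absolute Grade 4 platelet limit 1,000 times too high: an evident exponent slip, but in a threshold that drives dose holds and restarts

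*Protocol*

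**What the plan says.** Protocol Section 7.2.1.1 grades hematologic toxicity in Cohorts 1 and 2 by the IWCLL 2008 scale, set out in Table 5. Platelet grades rest on the percentage fall from the pretreatment value, and no grade is recorded unless the count is below normal. Footnote a adds an absolute limit: "If platelet count is $<20 \times 10^{12}/L$, this will be considered Grade 4 toxicity".

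Two other places give an absolute Grade 4 limit:

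- Protocol Section 6.5, in the DLT definition: "Grade 4 thrombocytopenia (platelet count <20,000" per microlitre.
- SAP Appendix C, note 2, on the same IWCLL 2008 scale. The sentence that starts "If, at any level of decrease, the platelet count is" gives the limit as 20 x 10^9/L and repeats it as 20,000/µL.

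The grades decide treatment. At Grade 3 or higher hematologic toxicity attributable to study drug, "acalabrutinib should be held until toxicity resolves to" Grade 1 or less, or to baseline. A further rule, after Table 6, says that "obinutuzumab and acalabrutinib should be held and complete blood count (CBC) monitored weekly". On recovery to the same level, "study drugs should be resumed with 1 dose level reduction".

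Low starting counts are allowed. Inclusion criterion 8 (Section 3.1) requires at least 50 x 10^9/L, but: "In subjects with CLL involvement of the marrow, $\geq 30 \times 10^9/\text{L}$ for Cohorts 1 and 2".

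**The concern.** The footnote contradicts another section of the same protocol and the SAP, and it is the operative grading text for holds, restarts and one-level dose reductions in Cohorts 1 and 2. No platelet count comes near 20 x 10^12/L, so the printed limit separates nothing. Taken at its word, it turns every attributable below-normal fall into a Grade 4 event. A reader who sees the slip and skips the line loses a limit that protects the subjects with the lowest starting counts.

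The rule may still be in use, since Section 6.7 lets subjects in Cohorts 1 and 2 stay on acalabrutinib to the end of the study.

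**Working it through.** **Units.** 1 L = 10^6 µL.

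- Section 6.5: 20,000/µL x 10^6 = 20 x 10^9/L, equal to SAP Appendix C.
- Table 5 footnote a: 20 x 10^12/L ÷ 10^6 = 20,000,000/µL.
- Ratio: 20 x 10^12 ÷ 20 x 10^9 = 1,000.

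**Grades under each limit.** Counts are in 10^9/L. The documents give no lower limit of normal. Where one is needed I assume 140 to 150, and the results are the same at both ends.

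| Pretreatment → current | Fall | Limit 20 x 10^9/L | As printed |
|---|---|---|---|
| 160 → 155 (normal) | 3% | no grade | no grade |
| 160 → 130 | 19% | Grade 1 | Grade 4 |
| 200 → 120 | 40% | Grade 2 | Grade 4 |
| 100 → 85 | 15% | Grade 1 | Grade 4 |
| 160 → 18 | 89% | Grade 4 | Grade 4 |

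**Hold and restart.** The correct hold is at a 50% fall (Grade 3), or below 20 if that is reached first. The correct Grade 1 restart is at a fall of 24% or less.

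- Pretreatment 100: hold at 100 x 0.50 = 50 or below; restart at 100 x 0.76 = 76 or above. As printed: hold at 99 or below, or at 89 or below if only falls of at least 11% are graded (100 x 0.89); restart only at 100.
- Pretreatment 50: hold at 25 or below; restart at 38 or above. As printed: hold at 49 or below, or at 44 or below on the 11% reading (50 x 0.89 = 44.5); restart only at 50.

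At pretreatment 100, counts of 51 to 99 (or 51 to 89) would trigger a hold wrongly. A recovering subject at 76 to 99 would be refused a restart that the intended rule allows.

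**Where the correct limit sets the hold.** The absolute limit holds at 19 or below. It matters only where the 50% line falls lower than that in whole counts.

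| Pretreatment | 50% line | Hold by percentage alone | Counts missed without the limit |
|---|---|---|---|
| 30 | 15 | 15 or below | 16–19 |
| 34 | 17 | 17 or below | 18–19 |
| 37 | 18.5 | 18 or below | 19 |
| 38 | 19 | 19 or below | none |
| 39 | 19.5 | 19 or below | none |

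So the range is 30 to 37. These counts are admitted only with marrow involvement. Section 6.5 does not cover them, because its platelet criterion applies to pretreatment counts above 50,000/µL.

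**Grade 3 band.** Table 5 gives 50% to 75% for Grade 3 and 75% or more for Grade 4, so a fall of exactly 75% fits both. Appendix C has 50% to 74%. Both grades trigger the hold, so no hold changes.

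**The case against.** The best case against is that nobody would apply the printed figure. Section 7.2.1.1 names IWCLL 2008 as the standard, Table 5 itself prints Grades 1 to 3, Section 6.5 gives the right limit, and the study runs at one site. A literal reading would also err towards holding drug, not towards dosing through severe thrombocytopenia. The literal cut-offs above therefore size a misapplication, not an expected effect. All of that stands, and it is why the practical risk is low. It does not make the footnote correct: Section 6.5 governs DLTs only, and skipping the line errs the other way for pretreatment counts of 30 to 37.

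A misread superscript in the extracted text cannot be excluded without the source page. It is unlikely, since the other platelet limits in this form (criterion 8, Table 14, SAP Section 10.0 and Appendix C) all read 10^9/L.

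A reader might infer more than the documents support:

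- That every platelet count becomes Grade 4. Normal counts are never graded.
- That restart becomes impossible. Return to baseline still permits it, and so does return to the normal range, where no grade is recorded.
- That any low count forces a hold. The toxicity must be attributable to study drug.
- That the reported safety tables are wrong. SAP Section 13.4.1 grades platelets by Appendix C and by CTCAE, and Protocol Section 14.6.1 tabulates by CTCAE. The summaries of dose withholding and reduction (SAP 6.3) and of AEs leading to dose modification or delay (SAP 13.1), and investigator-assigned grades, would be affected only if the slip had been followed literally.

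**Conclusion.** The footnote is wrong as written, by a factor of exactly 1,000, in text that sets holds, restarts and dose reductions for Cohorts 1 and 2. Literal use would bring forward attributable holds and close the Grade 1 restart route below the normal range. Disregarding the line would hold too late at whole pretreatment counts of 30 to 37 x 10^9/L, by at most four count units (16 to 19). It should be corrected, but it is not evidence of harm: DLT decisions, SAP-derived laboratory grades and the CTCAE tabulation are unaffected, and nothing in the documents shows that any subject was misgraded. The conclusion assumes that the source page carries the exponent 12. The examples at pretreatment 100 and 50 assume only that those counts are below the laboratory's normal range.

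**What to change.** Check the source page. If it reads as extracted, change footnote a to <20 x 10^9/L (20,000/µL), matching Section 6.5 and SAP Appendix C. In the same correction, change the Table 5 Grade 3 band to 50%–74%, as in Appendix C. The cost is one exponent and one band edge in the protocol, with no change to the SAP. Optionally, look briefly at investigator-assigned Grade 3 and 4 platelet events in Cohorts 1 and 2 to confirm that the intended limit was used.
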